University Hospital Southampton NHS Foundation T Southampton General Hospital [name] [contact]

Trial Site and Sponsor:

University Hospital Southampton NHS Foundation Trust (Research and Development) Southampton General Hospital [name]

Funding:

Equipment and consumables are provided by BioFire Diagnostics, [name].

Supported by NIHR Clinical Research Network, Wessex

Contents

- 1. Synopsis
- 2. Abbreviations
- 3. Background and Rationale
- 4. Objectives
- 5. Study Design and Methods
- 6. Recruitment / screening / inclusion / exclusion criteria
- 7. Further information regarding the FilmArray Gastrointestinal Panel
- 8. Analysis
- 9. Safety
- 10. Statistical Evaluation
- 11. Ethics and Approvals
- 12. Data management
- 13. Finances and indemnity
- 14. Other personnel
- 15. Laboratory study plan
- 16. Role of BioFire
- 17. References

1. Synopsis

Trial location

Single centre. University Hospital Southampton NHS Foundation Trust, Southampton General Hospital, [name]

Design

Pragmatic randomised controlled trial with 1:1 allocation to intervention or control arm

Population

Adults aged 18 years old and over presenting to the Acute Medical Unit, Acute Surgical Unit or Emergency Department or inpatient wards with acute diarrhoea and or vomiting (<14 days duration)

Sample Size

300 participants (150 per group)

Intervention

Stool sample and/or rectal swab tested for gastrointestinal pathogens using the FilmArray Gastrointestinal Panel (BioFire Diagnostics) with results communicated to clinical team

Control

Standard clinical care alone

Key Assessment

Subsequent retrospective hospital case note evaluation of clinical data

Primary Objective

Clinical impact assessment

Secondary Objectives

Evaluation of performance of FilmArray Gastrointestinal Panel

Timing

Three years or enrolment of 300 participants, whichever occurs soonest, with a minimum duration of one year (Participant Recruitment) (With a further five years for laboratory analysis only).

Study Overview

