The initial phase of this study was designed as an internal pilot study with exploratory outcomes and accurate samples size calculations were not possible. After recruiting 100 patients (50 per group) we now have accurate data on the mean and standard deviation of duration of side room use, and withdrawal rate, allowing us to calculate samples size needed for the primary outcome. 141 patients per group will give 90% power at a 0.05 significance level to detect a 1 day reduction in the mean duration of side room use; from 3 to 2 days (with a standard deviation of 6.7 days).⁴ This reduction is be considered clinically and economically significant. Allowing for a ~5% withdrawal rate we will recruit 150 patients per group (300 in total).

Recruitment numbers

300 participants will be recruited and randomised 1:1 intervention to routine clinical care, i.e. 150per group

9. Safety

The risks of stool samples, rectal swabs, vomitus samples and additional blood tests being taken are minimal and where occurring are likely to be of very low impact.

An Adverse Event (AE) is any untoward medical occurrence – there does not need to be a causal relationship between the occurrence and the study.

A Serious Adverse Event (SAE) is any adverse event that

- Results in death
- Is life threatening
- Requires hospitalisation or prolongation of existing hospitalisation
- Results in persistent or significant disability or incapacity
- Consists of a congenital anomaly or birth defect

As participants in ED are not yet hospitalised but have a reasonable likelihood of being admitted to hospital, patients enrolled in ED who are subsequently admitted to the hospital will not automatically be counted as having experienced a SAE.

Participants who are already admitted to AMU/ASU are already hospitalised however, an adverse event leading to prolongation of their existing hospitalisation would count as a SAE.

In the event of a SAE, the PI will be involved in deciding whether this was a study-related event.

SAEs occurring more than 30 days after the patient has left hospital will not be recorded or reported as SAEs because of the time lapsed in relation to the event and an acute infection or POC testing.

10. Statistical Evaluation

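### The sample-size sentence contradicts itself: 141 per group gives 90% power for a 1-day reduction if 6.7 is a variance, but about 24% if it is the standard deviation it is called

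*Protocol*

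**What the plan says.** The calculation is in Protocol section 8, under the sample size and power heading. It states that "141 patients per group will give 90% power at a 0.05 significance level", the aim being "to detect a 1 day reduction in the mean duration of side room use; from 3 to 2 days". The SD is given in the same place: "from 3 to 2 days (with a standard deviation of 6.7 days". The inputs are attributed to the first 100 patients (50 per group), with the statement that "we now have accurate data on the mean and standard deviation of duration of side room use". The sentence also carries reference marker 4, which section 17 lists as an aetiology cohort of hospitalised adults with gastroenteritis.

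An allowance of about 5% for withdrawal takes 141 to 150 per group, and the Synopsis repeats the result as "300 participants (150 per group". Whether the test is one- or two-sided is not stated. Section 10 compares the primary outcome by Student's t-test or the Mann-Whitney U test, whichever is appropriate. No other place in the protocol gives a different SD, a variance or another target difference.

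**The concern.** The target difference is 1 day and the stated SD is 6.7 days, a standardised difference of 1/6.7 = 0.15. An effect that small normally needs many hundreds of patients per group, so 141 per group for 90% power stands out at once.

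This is the only quantitative justification for the size of the trial. It supports the version 2.0 amendment, which turned the pilot into a full trial and raised the target from 200 to 300, and it supports the power claim for the primary outcome. If 6.7 days really is the SD, a true saving of one day, which the protocol regards as worthwhile, would be missed by a two-sided t-test about three times in four, and the result could be misread as no effect. No interim analysis is planned at which the discrepancy would come to light.

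**Working it through.** **Inputs, all from Protocol section 8.** 141 per group, 1:1 allocation; power 90%; significance level 0.05 (two-sided assumed, one-sided also tried); difference 3 − 2 = 1 day; SD 6.7 days; withdrawal about 5%.

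**Formula for two means.** n per group = 2 × (z_alpha + z_beta)² × SD² / difference². With two-sided 0.05 and 90% power, (1.960 + 1.2816)² = 10.507.

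**1. Attempt to reproduce 141 from the figures as stated.**
- 2 × 10.507 × 6.7² / 1² = 2 × 10.507 × 44.89 = 943.3, so 944 per group (945 by the exact t-test calculation). Not reproduced.
- One-sided 0.05 at 90% power: 769 per group.
- Two-sided 0.05 at 80% power: 705 per group. One-sided at 80%: 556.
- One-sample formula: 472.
- SDs proportional to the means (6.7 and 4.47): 682 per group.

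**2. What does give 141.**
- With 6.7 in place of SD²: 2 × 10.507 × 6.7 = 140.8, so 141.
- Solving for the SD that 141 implies: sqrt(141 / (2 × 10.507)) = 2.59 days, and sqrt(6.7) = 2.588.
- Power at 141 per group with SD 2.588: 90.0% (normal approximation), 89.8% (exact t).

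**3. What 141 per group delivers if the SD is 6.7 days.**
- Standard error of the difference: 6.7 × sqrt(2/141) = 0.798 days.
- Two-sided power for 1 day: about Φ(1/0.798 − 1.960) = Φ(−0.707) = 24.0% (exact t 23.9%). At 150 per group: 25.2%.
- One-sided power at 141 per group: 34.8% (exact t 34.7%).
- Difference detectable with 90% power: 3.2415 × 0.798 = 2.59 days, against a control mean of 3 days. With 80% power: 2.24 days.
- Expected 95% confidence interval half-width: 1.96 × 0.798 = 1.56 days (1.52 at 150 per group).

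**4. The withdrawal step.** 141 / 0.95 = 148.4, so 149, rounded to 150. This step is sound; the 300 in the Synopsis simply inherits the 141.

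**5. Sensitivity to the test.** The protocol gives no distribution, so the shapes here are assumptions. Simulations with 141 per group, means 3 and 2 and control SD 6.7 gave:

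| Assumed shape | Mann-Whitney power | t-test power |
|---|---|---|
| Log-normal, SD 6.7 in both groups | about 99% | about 40% |
| Log-normal, SD proportional to mean | about 70% | about 40% |
| Gamma, SD proportional to mean | about 16% | about 31% |
| Log-normal with 30% or 50% zeros, SD proportional to mean | about 28% or 14% | about 39% or 35% |

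The t-test stays far below 90% in every case. The Mann-Whitney result depends almost entirely on the assumed shape.

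**The case against.** The strongest reply is that this is only a labelling slip. The variance reading lands exactly on 141 and was the only standard variant tried that did, so a sound sample size under a wrong label is a strong candidate. That stands, and it rules out a reading that a reader might draw from the arithmetic: that the trial's actual power is 24%. The protocol does not support that as a fact; it holds only if 6.7 is the SD. Nor does it establish the benign reading. The figure is called an SD and given in days, and the same 141 would result if a true SD of 6.7 had been entered without being squared.

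A reader might also infer that 141 can arise only from treating 6.7 as a variance. That goes too far: any SD near 2.59 gives 141, so a misprinted SD is possible too.

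A third reply is that section 10 allows the Mann-Whitney test. A non-negative duration with mean 2 to 3 and SD 6.7 must be strongly right-skewed, which is where that test might be chosen. This does not rescue the sentence, which is about a reduction in the mean. It does limit the consequence: even with an SD of 6.7, one cannot say that a non-significant primary result is to be expected whichever test is used.

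Finally, reference 4 sits oddly beside inputs said to come from pilot patients. A reader might conclude that it is simply wrong and should go. The protocol does not show what the marker was meant to support, so it is a query and secondary to the arithmetic.

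**Conclusion.** The point holds in conditional form. As written, the sample-size sentence is wrong, because its five figures are mutually inconsistent for a comparison of means, one- or two-sided. If the SD is 6.7 days, the requirement is about 944 per group, 6.7 times the planned 141, and power for 1 day is about 24% (two-sided t-test, roughly normal theory). If 6.7 is the variance, or the SD is otherwise about 2.6 days, power is about 90% and the sample size stands. The protocol does not decide between these; the pilot data can. Because the power claim for the primary outcome rests on this one line and checking it is cheap, it must be corrected.

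**What to change.** Recompute the within-group SD of side-room time from the 100 pilot patients, then amend section 8 according to the result.

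- **If 6.7 is the variance, or the SD is about 2.6 days:** state the SD as 2.6 days. The 141 and 150 per group stand.
- **If 6.7 days is the SD:** restate the power for the planned numbers as about 24% at 141 and 25% at 150 per group for a 1-day reduction (two-sided t-test), with 90% power only for about 2.6 days and an expected 95% confidence interval half-width of about 1.6 days at 141 per group. Add that Mann-Whitney power would depend on a distribution the protocol does not give. Whether to revisit the sample size or the target difference is then for the sponsor to decide.

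In either case, state whether the 0.05 level is one- or two-sided, check whether reference 4 is the right source for the sentence, and correct the marker if it is not.

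The cost is one check of data already held and one corrected sentence. The correction itself requires no additional patients.

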A stool sample from a patient with acute diarrhoea presenting to hospital in England would conventionally undergo a range of laboratory testing methods for different pathogenic organisms. The key methods include microscopy, culture, enzyme immunoassay and PCR.⁹ These methods vary in their turnaround times but culture takes several days to generate a result to clinicians. These slow turnaround times mean that patients presenting with suspected gastroenteritis are isolated and often treated with antibiotics empirically leading to unnecessary isolation facility use in those without infection and antibiotic usage in those without bacterial aetiology.

In addition, conventional diagnostic testing is not comprehensive and is insensitive for many pathogens leading to many missed diagnoses and lack of confidence in a negative result.

Potential benefits of molecular point-of-care testing in acute gastroenteritis

Improved pathogen detection compared to conventional testing

A pan-European observational study showed the pathogen detection rate in stool samples from patients with gastroenteritis could be improved from 18% using traditional methods, to 54% using the multiplex rapid PCR FilmArray Gastroenteritis Panel. Site selection bias, a mix of adult and paediatric and inpatient and outpatient populations and heterogeneous local testing methods weaken the findings. Nevertheless, this multicentre, cross-sectional study clearly shows a wide spectrum of pathogens were detected; 20 different GI pathogens were detected, out of 22 tested for, in around 700 stool samples.¹⁰

Other studies have suggested similar improvements in diagnostic yield, including a USbased study of 230 prospectively collected stool samples, with 8.3% positivity with conventional diagnostics compared to 33.3% positivity with the FilmArray GI panel. Again, a broad range of pathogens were observed.¹¹

A paediatric-based study comparing the aetiologic yield of standard-of-care microbiologic testing ordered by physicians with that of the multiplex FilmArray GI panel, showed that identification of a pathogen increased from 46% to 65%.¹² This suggests a syndrome-based approach to testing may be clinically beneficial.

Decreased length of hospitalisation

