Consent is discussed and agreed as per the separate consent form and participant information sheet from potential participants, in-line with the inclusion and exclusion criteria. Blinding is not employed as it is impractical and would obstruct study methods. The study will take place across at least one year to include the peak periods of seasonal pathogens.

Randomisation

Participants will be enrolled and assigned a participant identification number consecutively. Once a patient has been screened and consented a study team member will log onto the password-protected electronic randomisation website (sealedenvelope.com, which uses randomised permuted blocks) to obtain a randomisation code for the patient who will then be allocated to either the intervention or control group.

For those randomised to the interventional arm:

A stool sample will be taken by a member of research staff (doctor or nurse). In the event of the patient being unable to provide a timely stool sample, a rectal swab will be obtained with appropriate chaperone as per hospital policy. The sample is placed in Carey-Blair media and analysed on the FilmArray using the Gastrointestinal Panel, as per training delivered by the apparatus manufacturer. Test results are generated in about 1 hour. In the event of a run failure, the analysis run will be repeated using the same sample; if there is insufficient sample left, further samples may be taken if the participant consents. If a rectal swab was

tested initially, a stool sample will be subsequently obtained at the earliest opportunity and then tested and the results checked to ensure concordance.

The results of the test will be documented in the patient's case notes. In the event of a pathogen being detected, a member of the clinical team responsible for the patient will be directly informed. The participant will also be informed of the result. If a positive result for a bacterial pathogen is detected the clinical team will be directed to the local and national treatment guidelines for that pathogen.

For all positive and negative results the infection and prevention control team and the site managers responsible for side room allocation will be informed in real time.

Further laboratory stool testing will be at the discretion of the responsible clinical team.

For those randomised to the control group

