The company product information sheet states "The FilmArray Gastrointestinal (GI) Panel tests for common gastrointestinal pathogens including viruses, bacteria and parasites that cause infectious diarrhea. *(sic)* The integrated FilmArray system brings sample to results in about an hour, with only 2 minutes of hands-on time."

The peer-reviewed published evidence relating to the diagnostic accuracy of the FilmArray Gastrointestinal Panel is discussed in the 'Background' section.

8. Analysis

The retrospective review of medical records will allow comparison of participants who received the rapid diagnostic test and controls managed with standard clinical care.

Primary outcome measure

• Duration of time in a side room

Secondary and exploratory outcomes

- Duration of time in a side room for pathogen positive patients
- Duration of time in a side room for pathogen negative patients

- Proportion of patients isolated in a side room
- Proportion of pathogen positive patients isolated in a side room
- Proportion of pathogen negative patients isolated in a side room
- Proportion of pathogen negative patients de-isolated
- Proportion of pathogen positive patient de-isolated
- Time to patient isolation in a side room
- Time to de-isolation in pathogen negative patients
- Proportion of patients treated with antibiotics
- Proportion of patients with bacterial gastroenteritis treated with antibiotics
- Proportion of patients without bacterial gastroenteritis treated with antibiotics
- Time to treatment with antibiotics
- Duration of antibiotics
- Duration of hospitalisation
- Proportion of patients with a pathogen detected
- Proportion of patients with bacterial pathogen detected
- Time to diagnosis
- Missed diagnoses
- Other medication use, complications (including acute kidney injury), ICU admissions, 30 day mortality, representation and readmission.
- Concordance between results obtained from rectal swab and stool culture
- Time from sampling to availability of results (Turnaround time)
- Patient satisfaction scores (using the modified NHS Adult Inpatient Survey Questionnaire 2016)

Sample size and power calculation

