This will be performed by the research team in conjunction with a dedicated medical statistician from the University of Southampton. Patients tested with the rapid molecular diagnostic test will be compared with patients treated using standard clinical care using standard descriptive and comparative statistical methods using Prism (GraphPad Software Inc; La Jolla, California) and SPSS (SPSS, Inc; Chicago, Illinois). The primary outcome measure of duration of time in side room isolation will be compared using the students t-test or Mann-Whitney U test as appropriate. The effect of group (intervention or control) on the primary outcome will be further assessed using logistic regression to control for demographics (age, sex) and relevant clinical variables.

Analysis will be by intention-to-treat. No interim analysis is planned. Trial results will be reported in accordance with the CONSORT statement. Missing data was minimal in the Cl's previous molecular POC RCT in secondary care and therefore expected to not be a significant issue.

11. Ethics and Approvals

Declaration of Helsinki

The Investigators will ensure that this study is conducted according to the principles of the current revision of the Declaration of Helsinki.

ICH Guidelines for Good Clinical Practice

The Investigators will ensure that this study is conducted in full conformity with the ICH Good Clinical Practice (GCP) and local regulatory requirements.

Informed Consent

Written, informed consent will be obtained, as per the informed consent form.

Submissions to HRA, REC and local R&D

The protocol, informed consent form, participant information sheet and GP letter (and any other document requested) will be submitted to the Health Research Agency (HRA) for their processes including Regional Ethics Committee (REC) for written approval, and the study will not commence until REC all necessary HRA approvals are in place. The Chief Investigator will submit and, where necessary, obtain approval from the REC for all subsequent substantial amendments to the protocol and informed consent document. Local R&D approval will be confirmed prior to study commencement.

Participant Confidentiality

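### The primary comparison of side-room time is unadjusted and leaves out side-room status at randomisation, giving up precision the trial could have at almost no cost

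*Protocol*

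**What the plan says.** Section 8 (Analysis) names the primary outcome as "Duration of time in a side room" and does not say when the clock starts. Section 10 fixes the test: "The primary outcome measure of duration of time in side room isolation will be compared using the students t-test or Mann-Whitney U test as appropriate". An adjusted analysis comes after it, in which the comparison between arms is "further assessed using logistic regression to control for demographics (age, sex) and relevant clinical variables". Side-room status at randomisation is not named.

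Allocation in section 5 (Randomisation) is through a website "which uses randomised permuted blocks"; no stratification factor is stated.

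Three other places bear on the point:

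- Section 3 (Conventional testing) says that, because results are slow, "patients presenting with suspected gastroenteritis are isolated and often treated with antibiotics empirically".
- Section 6 allows recruitment from ED, AMU, ASU and inpatient wards up to 48 hours after triage or arrival.
- Section 5 lists isolation facility use among the data taken from case notes, and section 8 lists "Time to patient isolation in a side room" as an outcome.

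**The concern.** With empirical isolation and a recruitment window of up to 48 hours, some patients can already be in a side room when they are randomised and others not. That status is fixed before allocation and is likely to predict side-room days. Permuted blocks without strata balance total numbers, not this status.

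A test with no covariate leaves the variation that status explains in the error term. The confidence interval for the difference in days is then wider than it need be, and the chance of detecting the 1-day reduction is lower. The follow-on model does not recover this. It comes after the primary test, and a logistic regression models a binary outcome, so it gives no adjusted difference in days.

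The variable should be obtainable without new data collection. Isolation times must be dated to produce the listed outcomes, and comparing them with the time of randomisation gives a yes/no status. This assumes that the electronic randomisation system records a time, which the protocol does not say.

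**Working it through.** **Inputs from the protocol (section 8, sample size).** 141 per group, 90% power, significance level 0.05, means of 3 and 2 days, SD printed as 6.7 days, about 5% withdrawal. Sidedness is not stated; two-sided is assumed.

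**The plan's own figure.** n per group = 2(1.960 + 1.282)² SD²/1².

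- SD 6.7: 2 × 10.507 × 44.89 = 943.4, so 944 per group. At 141 per group, power is about 24%.
- Variance 6.7 (SD = √6.7 = 2.59): 2 × 10.507 × 6.7 = 140.8, so 141 per group. 141/0.95 = 148.4, consistent with recruiting 150.

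The stated 141 is reproduced only if 6.7 is read as a variance. That contradiction is a separate matter; both readings are carried below.

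**Effect of adjustment.** Residual SD = SD × √(1 − rho²), where rho is the correlation between status and side-room days. For a yes/no status with a share p isolated and a difference d in mean days between the two kinds of patient, rho = d√(p(1 − p))/SD. The protocol gives none of rho, p or d, so a range is shown. Power is from the noncentral t distribution, 141 per group, 1-day difference, two-sided 0.05.

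| rho (assumed) | SD 2.59: residual SD | power | SD 6.7: residual SD | power |
|---|---|---|---|---|
| 0 | 2.59 | 89.8% | 6.70 | 23.9% |
| 0.3 | 2.47 | 92.3% | 6.39 | 25.8% |
| 0.37 | 2.40 | 93.6% | 6.22 | 27.0% |
| 0.5 | 2.24 | 96.2% | 5.80 | 30.3% |

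At rho 0.5 the 95% CI half-width falls from 0.61 to 0.53 day (SD 2.59) or from 1.57 to 1.36 days (SD 6.7).

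**Which rho is attainable?** Durations cannot be negative. With overall mean m, those not isolated have mean m − pd ≥ 0, so d ≤ m/p and rho ≤ (m/SD)√((1 − p)/p). Take m = 2.5 days, midway between 3 and 2.

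- SD 6.7, p = 0.5: d ≤ 5.0 days, rho ≤ 2.5/6.7 = 0.37, power at most 27.0%.
- SD 6.7, p = 0.7: d ≤ 3.57 days, rho ≤ 0.24, power at most 25.1%.
- SD 2.59, p = 0.5: rho 0.3 needs d = 0.3 × 2.59/0.5 = 1.55 days, and rho 0.5 needs d = 2.59 days. Both are below the 5.0-day limit.

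For p below one half the ceiling under SD 6.7 is higher (0.75 at p = 0.2), but rho 0.5 would then need d = 0.5 × 6.7/0.4 = 8.4 days.

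**Validity.** Simulations with normal outcomes (8,000 runs each, p = 0.5, d = 1 to 3 days) gave a type I error of about 5% for both the unadjusted and the adjusted test. With variance 6.7 and d = 2, power rose from 89.7% to 93.7%; with SD 6.7 and d = 2, only from 23.5% to 24.0%.

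**The case against.** The strongest reply is that nothing here is invalid. An unadjusted two-group test in a randomised trial is unbiased over randomisations and holds its error rate, and the sample size used the total SD, which already contains any variance due to isolation status. On the variance reading, power is already about 90%. All of that stands, and it limits the point to efficiency.

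Four stronger readings are tempting, and the protocol does not support them.

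- *Chance imbalance in isolation status biases the result or is a second loss.* With half isolated and 141 per group, the SD of the between-arm gap is √(2 × 0.25/141) = 6.0 percentage points, and a gap of 10 points or more has probability of about 9%. With d of 2.5 days (assumed), a 10-point gap moves the estimate by 0.25 day, less than one standard error (0.31 day at SD 2.59; 0.80 at SD 6.7). This is the same sampling error already in the unadjusted standard error.
- *The adjusted analysis is confined to age and sex.* It is to "control for demographics (age, sex) and relevant clinical variables". That open class could include side-room status, and a SAP may say so. The primary test would still be unadjusted, and the model still logistic.
- *Adjustment would rescue the power.* With SD 6.7 as printed, even rho 0.5 leaves power at 30.3%.
- *The gain is assured.* If nearly all suspected cases are already isolated, the covariate hardly varies. If time counts from randomisation, patients isolated earlier may have used part of their stay. The protocol settles neither.

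It is also fair to say that choosing a primary covariate now is more than a wording change, because section 8 shows that side-room data from the first 100 patients have been examined in an open-label trial.

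**Conclusion.** The point holds as a loss of precision, not of validity. The protocol itself fixes a primary test that takes no covariate, states no stratification factor, and offers as its only adjusted analysis a model that does not estimate days.

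The benefit is material mainly if 6.7 is a variance: about 2.5 points of power at rho 0.3 and 6 points at rho 0.5, from 89.8%. With the SD as printed, half or more isolated at randomisation and a mean of about 2.5 days, it is at most about 3 points from 23.9%. These figures rest on assumed correlations, a two-sided test and 141 analysed per group. The mismatch between SD 6.7 and 141 per group is larger, separate, and not repaired by adjustment.

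**What to change.** In section 10, make the primary estimate the mean difference in side-room days from a linear model on randomised group, with side-room status at randomisation (yes/no) as a pre-specified covariate. Use robust or bootstrap standard errors to allow for skew, and report the 95% CI. Derive the status from the abstracted isolation times and the randomisation time stamp. It must be the status at randomisation, because later isolation can be affected by the test result. Keep the planned unadjusted comparison as a supporting analysis. Age and recruiting area may be added but are optional; no benefit has been calculated for them.

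The cost is one derived variable and one degree of freedom, with no extra patients or visits. Little is gained if the correlation is low or nearly all patients are already isolated. Because data from the first 100 patients have been seen, the amendment should be dated and should justify the covariate without reference to results by arm.

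### The adjusted analysis of the primary outcome names logistic regression, which does not fit a duration in days and gives no adjusted difference in days

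*Protocol*

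**What the plan says.** Section 8 of the protocol lists one primary outcome measure: "Duration of time in a side room". The sample size paragraph in the same section treats it as a quantity with a mean; the aim is to "detect a 1 day reduction in the mean duration of side room use; from 3 to 2 days".

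Section 10 first gives the main analysis: "The primary outcome measure of duration of time in side room isolation will be compared using the students t-test or Mann-Whitney U test as appropriate". It then adds a covariate-adjusted analysis of the same outcome: "The effect of group (intervention or control) on the primary outcome will be further assessed using logistic regression to control for demographics (age, sex"), together with clinical variables that it does not list.

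Side-room measures that are binary by nature, such as the proportion of patients isolated and the proportions de-isolated, appear in section 8 as separate secondary outcomes.

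**The concern.** Logistic regression models the odds of falling in a category. Its binary form needs an outcome with two values, and its ordinal form needs ordered categories or ranks. The primary outcome is neither as defined: it is a length of time. The analyst who follows section 10 to the letter cannot fit the named model to the named outcome. To make it run, something absent from the protocol must be added, such as a threshold number of days, a set of ordered categories or a statement that an ordinal model on ranked durations is meant.

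At stake is the meaning of the adjusted result. The protocol expresses its target as a difference in mean days. Whichever way the logistic model is rescued, it reports an odds ratio, which cannot be read against that target. No other covariate-adjusted analysis of the primary outcome is stated.

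**Working it through.** **1. The target and its scale.** Inputs from section 8: means of 3 and 2 days, "with a standard deviation of 6.7 days", and "141 patients per group will give 90% power at a 0.05 significance level". For a two-sided comparison of means, n per group = 2 × (1.960 + 1.2816)² × SD² / (difference)².

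- SD 6.7, difference 1: 2 × 10.508 × 44.89 = 943.4, so 944 per group. The stated 141 is not reproduced; at 141 per group the power would be about 24%.
- 6.7 read as a variance (SD = √6.7 = 2.59): 2 × 10.508 × 6.7 = 140.8, so 141 per group, as stated.

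The mismatch is a separate matter. It matters here for two reasons. Under either reading the calculation is for a difference in mean days, so the outcome is a quantity and not a category. And 90% is not a safe baseline from which to count a loss of power.

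**2. The passages side by side.**

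| Place | How the primary outcome is treated |
|---|---|
| Section 8, primary outcome | a length of time |
| Section 8, sample size | a mean in days with a standard deviation |
| Section 10, main comparison | a quantity or ranked quantity (t-test or Mann-Whitney U) |
| Section 10, adjusted analysis | an outcome for logistic regression |

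The last row does not fit the other three. No cut-off, binary version, ordered categories or mention of ordinal regression appears in the protocol. The adjusted-analysis sentence names the primary outcome, so it cannot be read as referring to the binary secondary outcomes.

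**3. Can the model be fitted as written?** Durations were simulated for 141 patients per group (assumed gamma shape, means 3 and 2, variance 6.7). A binary logit was refused because the outcome must lie between 0 and 1. Linear regression on the same data ran and returned a group difference of −0.90 days, against a true value of −1.

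**4. Does an odds ratio correspond to 1 day?** Suppose a cut-off c were added. Let p be the probability of exceeding c in each group; then the odds ratio is [p₂/(1 − p₂)] / [p₁/(1 − p₁)], with group 1 at a mean of 3 days and group 2 at 2 days. Example for a gamma shape with SD 2.59 and c = 3: p₁ = 0.386 and p₂ = 0.224, so (0.224/0.776)/(0.386/0.614) = 0.289/0.629 = 0.46. The shapes and cut-offs below are assumptions, used only to show the range.

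| Assumed shape and SD | c = 1 day | c = 3 days | c = 5 days |
|---|---|---|---|
| Gamma, 2.59 | 0.30 | 0.46 | 0.56 |
| Lognormal, 2.59 | 0.22 | 0.41 | 0.50 |
| Gamma, 6.7 | 0.45 | 0.50 | 0.54 |
| Lognormal, 6.7 | 0.44 | 0.51 | 0.54 |

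A normal shape allows negative durations and so is unsuitable here. It gives 0.50 to 0.54 at SD 2.59 and 0.78 to 0.79 at SD 6.7. The difference in means is 1 day in every cell. The odds ratio moves with the cut-off, the shape and the spread, so it cannot be converted back to days.

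**The case against.** **It is a supporting analysis.** The main test is the t-test or Mann-Whitney comparison, and the regression only assesses the outcome further. With 1:1 randomisation the unadjusted comparison is valid without covariates, and a difference in mean days can be taken from it. This stands, and it limits the weight of the point.

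**Ordinal logistic regression may have been meant.** It can be applied to ranked durations without choosing a threshold, and it is a natural partner to the Mann-Whitney test. This stands in part. The blunt statement that logistic regression cannot model a duration holds for the binary form only. But the protocol does not say ordinal, and that model too returns an odds ratio.

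**The SAP may settle it.** A covariate list or a cut-off is commonly left to the SAP, and none is shown. That excuses missing detail. It does not excuse naming a model that does not match the outcome.

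Three stronger readings are tempting and are not supported:

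- A reader might infer that a cut-point will be picked after the data are seen. The documents do not show this; a cut-point could be fixed in advance elsewhere.
- A reader might infer a stated loss of power from splitting the duration. Any such figure rests on a distribution and a cut-off that the documents do not give, and on a true 90% baseline that an SD of 6.7 days does not deliver. Moreover, no power is claimed for the adjusted model.
- A reader might infer that the clinical or economic conclusion would have no estimate in days. Nothing ties the economic evaluation to the adjusted model, and the unadjusted difference in mean days can serve.

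**Conclusion.** The point holds as a plain mis-specification. Section 10 assigns logistic regression to an outcome that the protocol everywhere else treats as a number of days, and it supplies nothing that would make the model applicable. Any odds ratio obtained by adding a cut-off or categories would not correspond to the "1 day reduction in the mean duration of side room use" on which the trial is sized.

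Its reach is the one stated covariate-adjusted analysis of the primary outcome. The main comparison, its type I error and the sample size are unaffected. It should be fixed before analysis, and it does not threaten the validity of the trial. The conclusion rests on the protocol's wording alone; the odds ratios under the working are illustrations under assumed shapes, and no numerical size in terms of power is claimed.

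**What to change.** In section 10, replace logistic regression for the primary outcome with a model for the duration itself. One suitable wording: the effect of group on side-room days will also be estimated by linear regression on group, age, sex and the pre-specified clinical variables, with a heteroscedasticity-robust or bootstrap 95% confidence interval, and reported as an adjusted mean difference in days. A gamma-type model that reports a mean difference would serve equally well; the choice between them is one of preference. The clinical variables still need to be named in advance, which the SAP can do.

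Keep logistic regression for the binary secondary outcomes, such as the proportions isolated, de-isolated or treated with antibiotics. If the team does want a logistic model for the duration, the protocol should say whether it is binary or ordinal, fix the cut-off or categories in advance, and accept that the result is an odds ratio.

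The cost is one sentence. No extra data are needed, and the sample size and main test do not change.
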